**Table 2: Outline of Visit Schedule Based on Age**

Visit	V1	V2	V3	V4	V5	V6	V7	V8	V9	V10	V11
Age at Randomization	Varies	Varies	Varies	2 months (60 days ±7)	4 months (120 days ±14)	6 months (180 days ±14)	9 months (270 days ±14)	12 months (365 days ±21)	15 months (455 days ±21)	18 months (545 days ±21)	21 months (635 days ±21)
Study Day	-14/1	8-15	22-29	Varies	Varies	Varies	Varies	Varies	Varies	Varies	Varies
≤ 15 days	X	X	X	X	X	X	X	X			
> 15 and ≤ 40 days	X	X	X		X	X	X	X			
> 40 days and ≤ 78 days	X	X	X		X	X	X	X	X		
> 78 days and ≤ 138 days	X	X	X			X	X	X	X		
> 138 days and ≤ 228 days	X	X	X				X	X	X	X	
> 228 days and ≤ 277 days	X	X	X					X	X	X	X

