### **10.2 SECONDARY OBJECTIVES**

The secondary objective is to compare the study drug and the control treatment by assessing frequency of dose adjustments, and growth patterns (length, BW, head circumference).

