## 13 TREATMENTS

### 13.1 STUDY DRUG (IP)

#### 13.1.1 DESCRIPTION OF STUDY DRUG

**Study Drug: Tirosint®-SOL (levothyroxine sodium) oral solution** (IBSA Pharma Inc.). Tirosint-SOL is a ready-to-use solution containing LT4. It is a clear, colorless to slightly yellow solution supplied in a 1 mL white, nontransparent, unit-dose ampule and is available in the following strengths (mcg/mL): 13, 25, 37.5, 44, 50, 62.5, 75, 88, 100, 112, 125, 137, 150, 175, 200. The inactive ingredients contained in the product are glycerol and water.

Tirosint®-SOL oral solution will be provided by the Sponsor at the following strengths: 13, 25, 37.5, 44, 50, 62.5, 75, 88, 100 mcg. This strengths range is considered sufficient based on the potential weight of the subjects enrolled in the study. However, additional strengths among those authorized for Tirosint®-SOL may be provided upon request in particular cases (e.g. obese subjects).

**Control: Crushed levothyroxine sodium tablets.** LT4 tablets will vary based on the Subject and SOC. Newly diagnosed neonates will start treatment with one of the FDA-approved LT4 tablets available on the market, as determined by SOC. Infants already on therapy will continue taking the same LT4 tablets that they are on as a prescription before inclusion in the study. Both branded and generic products will be allowed in the study, the choice being left to the PI.

Any change in source of the LT4, especially if not a standard brand, requires repeat TFTs (serum T4 and TSH) two to six weeks after the change to assess for the potential retitration of the dose ([AAP 2006](#), [Van Trotsenberg 2021](#), [Rose 2023](#)). This situation should be avoided when possible.

LT4 tablets are commercially available at the following strengths: 25, 50, 75, 88, 100, 112, 125, 137, 150, 175, 200, and 300 mcg. Inactive ingredients vary between formulations.

LT4 tablets will **NOT** be supplied by the Sponsor. Tablets will either be provided by the site hospital pharmacy or purchased by the parent/guardian of the subject at a local pharmacy and reimbursed. Any strength, among the commercially available ones, can be used in the study, though it is expected that the following strengths will most commonly be utilized: 25, 50, 75, 88, 100 mcg. If needed, tablets can be cut in halves to obtain the missing intermediate strengths, for example:

- 37.5 mcg daily dose will be obtained as half 75 mcg tablet;

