### 16.2.2 LONG-TERM FOLLOW-UP PHASE

The long-term follow-up phase begins once TFTs normalization has been achieved and includes Visits 4 to 11.

If a change in LT4 dose is needed or, at the discretion of the Investigator, if an abnormal T4 or TSH are found, an additional follow-up visit should be performed 2-6 weeks after the dose change or abnormal finding (e.g. Follow-Up Type 2, FU2). If the timing of FU2 visit overlaps with the next planned visit (V5-V11), it is possible to perform only the planned visit.

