### **19.3.4 SAFETY OUTCOMES**

Vital signs at each in-person visit will be analyzed descriptively within treatment groups.

Length, weight and head circumference will be analysed at each in-person visit by means of basal value, treatment group, newly diagnosed neonates vs infants already on LT4 therapy, age at inclusion and center as covariate.

The presence of signs and symptoms of hypo- and hyper-thyroidism at each planned visit will be compared between treatment groups by means of Chi test.

Number of subjects experiencing AEs and SAEs during the study will be calculated. Number of AEs and SAEs will also be calculated. Difference between treatment groups on subjects who experienced AEs and SAEs will be evaluated using a Chi test or a two-tailed Fisher's exact test as appropriate. Moreover adverse events will be described by MedDRA's System Organ Classes (SOCs) and Preferred Term (PT).

Similar summary tables will be provided for the number of AEs/SAEs at least possibly related to study treatment and for the number of AEs/SAEs leading to study discontinuation.

The number and percentage of subjects with AEs/SAEs will be summarized by their MedDRA preferred term within SOC.

Any subject reporting multiple episodes of the same AE/SAE (i.e. same preferred term) will be counted once.

Compliance will be calculated as the percentage of medication taken in relation to the recommended dose and the actual period of treatment (number of doses reported to be taken / number of doses envisaged x 100). Treatment Compliance will be described by means of descriptive statistics.

The number of subjects who need a dose re-adjustment during the long-term follow-up phase of the study will be compared between treatment groups by means of Chi test.

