6.1.2 Secondary efficacy variables

Laboratory parameters

- Thyroid Stimulating Hormone (TSH);
- Free Thyroxine (FT4);
- Number of events of TSH values above 4.5 mU/L;
- Number of events of FT4 values below the middle of the laboratory normal range

Frequency of dose adjustments

Percent number of subjects (%) who need a dose adjustment in the long-term follow up phase.

Parents' satisfaction questionnaire (PSQ)

The Parents' Satisfaction Questionnaire is completed by the parents/guardian in the eDiary:

at V1 only for infants who are already on TH therapy, and 0-3 days before in-clinic visits for all subjects.

Parents answer questions about the following topics:

- Coping and mental well-being;
- Drug preparation & administration;
- Treatment satisfaction; and
- Medication preference.

The PSQ score at each visit will be computed as sum of all questions scores assigned as reported in Appendix 3.

Caregiver administered Children's Acceptance Tool (CareCAT)

This questionnaire is completed within the eDiary during the first, the third and the eighth week of treatment.

Descriptors:

Swallows well – Medicine is swallowed down

- Observing the act of swallowing the medicine – '[I see that she] drinks the medicine and swallows'
- Ingesting the medicine in absence of negative behaviors – 'He swallows and does not give me a hard time'

Refusal – Resistance of the child (e.g. fighting, crying)

- Defensive behavior preventing the intake of medicine – 'By pushing the spoon' or 'fights with her hands' or 'turns away her head'
- Spitting up – Some medicine is coming out of the mouth immediately
- Forcing the medicine out actively – 'He spits or maybe blows the medicine out'
- Medicine passively leaving the mouth ('overflow' or 'spilling') – 'When the medicines runs down the mouth'

Vomiting – Within 30 minutes after swallowing the medicine the child brings up something [vomits]

- 'She takes out the medicine after feeling nauseous, then vomits it with food'

Medication not taken – No medicine went into the mouth of the child

- No oral intake of medicine – 'She does not want [to take the medicine] until the medicine did not get in [the mouth]'
- Intake without ingesting – 'I have tried to give her but [the medicine] was still not swallowed'

Growth assessments

The following variables about growth are collected: length (cm), weight (Kg) and head circumference (cm).

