The mixed model will be adjusted with Kenward-Roger method and the unconstructed covariance matrix will be used as first choice (other matrixs will be considered if there will be convergence problems).

Summary descriptive statistics will be provided for Parents’ Satisfaction Questionnaire score and the results at each visit will also be compared between treatment groups by Wilcoxon Mann-Whitney test.

Caregiver Administered Children’s Acceptance Tool (CareCAT)

The subject medicine acceptance assessed by “Caregiver Administered Children’s Acceptance Tool (CareCAT)” will be analyzed during the first week, the third week, and the eighth week

of administration and analyzed by day in each week and by week comparing the treatment groups by means Cochran-Mantel-Haenszel χ^2 test. Descriptive statistics on aggregate CareCAT results overall and by week will also be provided.

Dose re-adjustment

The number of subjects who need a dose re-adjustment during the long-term follow-up phase (Visit 4 to Visit 11) of the study will be compared between treatment groups by means of Chi-squared test or, when the expected values in any of the cells of a contingency table are below 5 or the total number of observations is less than 20, Fisher exact test as appropriate.

Growth pattern

Summary descriptive statistics on length (cm), weight (Kg) and head circumference (cm) will be provided. Results at each visit for each parameter will be compared between treatment groups by Wilcoxon Mann-Whitney test.

Growth assessment parameters will also be listed with clinically significant information.

Signs and symptoms of hypo- and hyper-thyroidism

Number of subjects experiencing hypothyroidism/hyperthyroidism signs or symptoms will be summarized by hypothyroidism, hyperthyroidism and overall.

The number of subjects experiencing at least one sign or symptom will be compared between treatment groups using a Chi-squared test or, when the expected values in any of the cells of a contingency table are below 5 or the total number of observations is less than 20, Fisher exact test as appropriate.

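### The dose-adjustment comparison starts at Visit 4, so it leaves out most of the weeks in which re-titration would be assessed after Treatment infants change formulation

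*SAP*

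**What the plan says.** Protocol 10.2 states the secondary objective as "assessing frequency of dose adjustments, and growth patterns", without restricting it to a phase. The Main Outcomes in the protocol synopsis list the same quantity, also without restriction.

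The analysis is narrower. Protocol 19.3.4: "The number of subjects who need a dose re-adjustment during the long-term follow-up phase of the study will be compared between treatment groups". SAP 6.1.2 defines the variable as "Percent number of subjects (%) who need a dose adjustment in the long-term follow up phase". SAP 9.4.2 adds the visit numbers: "The number of subjects who need a dose re-adjustment during the long-term follow-up phase (Visit 4 to Visit 11) of the study".

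The phase is defined in Protocol 16.2.2: "The long-term follow-up phase begins once TFTs normalization has been achieved and includes Visits 4 to 11". Protocol 16.2.1 puts Visits 2 and 3, and any FU1 visits, in the normalization phase, and Table 1 labels the columns the same way. Dose changes are allowed at Visit 2, Visit 3 and FU1 (Protocol 16.2.3 to 16.2.5), but neither document plans a between-arm count of them.

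Under Protocol 13.1.1 and 13.1.2, infants randomised to Treatment go directly from crushed tablets to the solution, while Control infants stay on the tablets they were already taking. On a change of LT4 source, Protocol 13.1.1 says that it "requires repeat TFTs (serum T4 and TSH) two to six weeks after the change to assess for the potential retitration of the dose". Protocol 11.2 also cites guideline advice to re-test 4 to 6 weeks after a change of dosage or formulation.

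**The concern.** The objective asks how often doses are adjusted; the analysis answers for the later part of follow-up only. The part left out is the one in which the arms differ by design among infants: one arm has just changed formulation and the other has not. Protocol 9.1 relies on titration during the switch when it calls the switching risk minimal, yet that titration is not counted. The SAP also treats the early period unevenly: TSH and FT4 events are aggregated from Visit 2 (SAP 9.4.2), but the dose changes that such results may prompt are not.

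At stake is whether the report can say how often a child already on tablets needs a dose change in the weeks after moving to the solution, compared with a child who stays on tablets.

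**Working it through.** The documents give no expected rate or sample size for dose adjustments, so there is no stated figure to reproduce. The check is one of timing, followed by an illustration on assumed rates.

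**1. Who is affected.** 31 randomised (SAP 3); 3 + 1 neonates (SAP 3.4). Infants already on LT4: 31 − 4 = 27, and 27/31 = 87%.

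**2. First counted planned visit for an infant.** In Table 2 only children randomised at 15 days of age or less have a Visit 4; infants are at least 29 days old. Days from randomisation = visit age − age at randomisation, using nominal visit ages of 120, 180, 270 and 365 days and windows of ±14 days (V5 to V7) or ±21 days (V8). The last row is the band "> 228 days and ≤ 277 days".

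| Age at randomisation (days) | First counted visit | Nominal (days) | With window (days) |
|---|---|---|---|
| 29–40 | V5 | 80–91 | 66–105 |
| 41–78 | V5 | 42–79 | 28–93 |
| 79–138 | V6 | 42–101 | 28–115 |
| 139–228 | V7 | 42–131 | 28–145 |
| 229–277 | V8 | 88–136 | 67–157 |

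Example, second row: 120 − 78 = 42 and 120 − 41 = 79; with the window, 106 − 78 = 28 and 134 − 41 = 93. Overall: 42 to 136 days nominal, 28 to 157 with windows.

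**3. Against the re-titration period.** Two to six weeks is 14 to 42 days.
- Visit 2 is 7 to 14 days after treatment start, so it only touches the period.
- Visit 3 is at 21 to 28 days, inside it.
- A first FU1, usually two weeks after Visit 3, falls at about 21 + 14 = 35 to 28 + 14 = 42 days, also inside it.
- At nominal ages the first counted planned visit is never before day 42. With windows it can fall inside the period only for infants randomised at 64–78, 124–138 or 214–228 days of age (106 − 64 = 42, 166 − 124 = 42, 256 − 214 = 42), and only if the visit is held early.

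**4. Illustration (all rates assumed).** The endpoint is subjects with any adjustment. If early and later adjustments are independent and the later rate is the same in both arms:

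all-period rate = 1 − (1 − later) × (1 − early)

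difference = (1 − later) × (early Treatment − early Control)

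The Visit 4 to 11 comparison then has an expected difference of 0 whatever the early rates. With an early Control rate of 10%:

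| Early Treatment | All-period, later 30% | Difference | All-period, later 50% | Difference |
|---|---|---|---|---|
| 10% | 37% vs 37% | 0 | 55% vs 55% | 0 |
| 20% | 44% vs 37% | 7 points | 60% vs 55% | 5 points |
| 40% | 58% vs 37% | 21 points | 70% vs 55% | 15 points |
| 60% | 72% vs 37% | 35 points | 80% vs 55% | 25 points |

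The sign can reverse: early rates of 10% in Treatment and 20% in Control, with a later rate of 30%, give 0.70 × (0.10 − 0.20) = −7 points.

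**5. What a test would add.** With all 31 children split 21:10 (assumed), the power of Fisher's exact test across the tabled scenarios is about 3% to 36%. The gain is in the estimate, not in a test.

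**The case against.** - **The limit comes from the protocol.** Protocol 19.3.4 restricts the comparison to the long-term phase, and the visit numbers match Protocol 16.2.1, 16.2.2 and Table 1. A reader might infer that the SAP contradicts the protocol's phase definition, because an infant with normal tests at entry could be in the long-term phase from the start. The documents do not support that: the tension between starting at normalization and listing visit numbers lies inside Protocol 16.2.1 and 16.2.2. Nor does either document say that the window was designed for neonates; 16.2.1 applies to all subjects.
- **Maintenance-phase adjustment is a legitimate, labelled question.** This stands, and is why the planned comparison should stay.
- **Control infants may be titrating too.** Entry needs only three weeks of LT4 and no normal result, and doses may be changed at inclusion (Protocol 12.1, 13.1.2). That Control loses few early changes cannot be assumed.
- **Some of the period is captured.** Counted visits can fall from day 28, and a planned visit (V4 to V8) may replace an overlapping FU1. The two-to-six-week sentence stands within the text on Control tablets; the guideline advice on formulation changes says 4 to 6 weeks. This shifts weight from Visits 2 and 3 towards FU1, but step 3 shows that most of the period is still uncounted.
- **Other analyses cover the early weeks.** TSH and FT4 events run from Visit 2, and LT4 dose/kg is compared by visit and by stratum. These help, but dose/kg also moves with weight and neither is a count of adjustments.
- **Everything is exploratory (SAP 9.4) and power is low.** True; this limits the weight of the point.

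**Conclusion.** The point holds as a gap between objective and analysis. The objective has no phase limit, but no between-arm count covers changes at Visit 2, Visit 3 or FU1. For the 27 infants the first counted planned visit comes 42 to 136 days after randomisation at nominal ages (28 to 157 with windows), so most of the two-to-six-week re-titration period is not compared. The timing rests on Table 2 and assumes that visits follow it.

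A reader might go further and infer that the comparison is biased in favour of the solution by a definite amount. The documents do not support this. They give no adjustment rates, so neither direction nor size can be stated; the claim is conditional on switching prompting extra changes. Assumed early rates of 30% and 10% would not mean a 20-point loss either: for subjects with any adjustment the difference is (1 − later rate) × 20 points, which is 14, 10 or 4 points at later rates of 30%, 50% or 80%.

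**What to change.** In SAP 6.1.2 and 9.4.2:

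- Keep the protocol-specified Visit 4 to Visit 11 comparison.
- Add, by arm and by neonate/infant stratum, the number and percentage of subjects with any dose adjustment from after the Day 1 dose to end of study, including Visit 2, Visit 3, FU1, FU2 and unscheduled visits. Split it into the first six weeks and thereafter. With 3 and 1 neonates, that stratum is descriptive only.
- Report changes made at inclusion separately.
- State how a change between Visit 3 and the next planned visit is classed.
- Label the table as added and exploratory. Note beside it that Visit 2 blood sampling is optional for infants and the trial is open-label, so early changes may be ascertained differently by arm.

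No new data collection is needed: Table 1 has a dosing evaluation at every planned and follow-up visit, and Protocol 13.1.2 requires all dosing schemes to be recorded in the EDC. The cost is SAP wording, one re-cut of the dosing data and one more exploratory table. The early Treatment-arm rate may look less favourable.

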### 12.1 INCLUSION CRITERIA

Subjects must satisfy all of the following criteria to be enrolled in the study:

1. Male and female subjects aged 0 to 9 months (277 days) at Inclusion;
2. Primary CH diagnosis with elevated TSH and low or normal FT4, requiring treatment with LT4, under either of the following conditions:
  - Neonates (aged 0 to 28 days) newly diagnosed with primary CH and needing to initiate LT4 therapy, or
  - Infants (aged 29 days to 277 days) previously diagnosed with primary CH and who are already on LT4 therapy for at least 3 weeks;
3. Parent or legal guardian of the subject provides voluntary written and informed consent prior to initiation of any study procedures; and
4. Parent or legal guardian of the subject is willing and able to comply with scheduled visits and all study activities.

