#### **16.2.4 VISIT 3 (STUDY DAY 22-29, i.e. 21-28 DAYS AFTER TREATMENT START)**

During Visit 3 the PI or designee will complete the following via an in-clinic visit:

- Verify concomitant medications;
- Record AEs;
- Perform a physical examination including body measurements and vital signs;
- Assess the presence of signs and symptoms of hypo- or hyper- thyroidism;
- Take blood samples for serum TSH, FT4 and, optional, TT4;
- Perform dosing evaluation;
  - A different LT4 dose may be indicated and drug dispensed or shipped to parents/guardians if the dose must be adjusted;
- Record nutritional intake;
- Review eDiary completion (Treatment Compliance, Parents' Satisfaction Questionnaire, CareCAT);
  - If needed, further instructions will be provided to the parent/guardian on how to complete the eDiary and how to comply with the study requirements;
  - Report and resolve discrepancies that are noted in treatment compliance;
- Return and dispense drug, if applicable; and
- Update the Subject Visit Reminder Card.

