2 VERSION HISTORY

| Version Number | Summary/Reason for changes | Date Issued |
|------------------|--|-------------|
| Draft 0.1 | First draft | 13/08/2025 |
| Final 1.0 | First final version | 15/10/2025 |
| Draft 1.1 | Section 7.1: LT4 medications will be summarized by Anatomical Therapeutic Chemical (ATC) level 2 and preferred drug name, separately from the prior and concomitant medications. Section 9.3: The demographic data analysis will be repeated stratified on neonates and infants. Section 9.4: The variables newly diagnosed neonates vs infants already on LT4 therapy and center will be removed from the analysis of covariances models. Interactions between visit and treatment group will be added to estimate the treatment effect at each visit. The visits included in the Parent Satisfaction Questionnaire analysis of covariance are specified. LT4 dose/kg, TSH and FT4 levels at each visit will be compared between treatment groups by Wilcoxon Mann-Whitney test. These comparisons will be repeated stratified on neonates and infants. | 09/03/2026 |

| | | |
|------------------|---|------------|
| | 
TSH values above 4.5 mU/L and FT4 values below the middle of the laboratory normal range will be analyzed also aggregate from Visit 2 to the last available visit.
 
Summary descriptive statistics will be provided for Parents' Satisfaction Questionnaire score and the results at each visit will be compared between treatment groups by Wilcoxon Mann-Whitney test. Descriptive statistics on aggregate CareCAT results will also be provided. During the first week, the third week, and the eighth week of administration CareCAT will be analyzed by day in each week and by week comparing the treatment groups by means Cochran-Mantel-Haenszel χ^2 test. Descriptive statistics on aggregate CareCAT results overall and by week will also be provided.
 | |
| Final 2.0 | 
Final version release.
 
Section 9.4.2: added growth pattern comparison between treatment groups by Wilcoxon Mann-Whitney test.
 | 24/03/2026 |

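### Growth is tested on raw cm and kg without the baseline and age covariates the protocol planned; the change is not listed, and it costs most precision at Visit 3

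*SAP*

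**What the plan says.** SAP 9.4.2, under Growth pattern, has two analysis elements. The first is descriptive: "Summary descriptive statistics on length (cm), weight (Kg) and head circumference (cm) will be provided". The second is the test: "Results at each visit for each parameter will be compared between treatment groups by Wilcoxon Mann-Whitney test". There is no baseline term, age term, sex term, standardized score or change from baseline. The version history shows that the test is recent and deliberate: "Section 9.4.2: added growth pattern comparison between treatment groups by Wilcoxon Mann-Whitney test".

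Protocol 19.3.4 planned something else: "Length, weight and head circumference will be analysed at each in-person visit by means of basal value, treatment group", followed by "newly diagnosed neonates vs infants already on LT4 therapy, age at inclusion and center as covariate". That sentence names no model, but a covariate-adjusted analysis is the only natural reading, and 19.3.2 uses the same covariates under analysis of covariance.

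SAP 3.4, which sets out changes from the protocol, covers protocol 19.2, 19.3.1, 19.3.2 and 19.3.3. It does not mention 19.3.4, where the growth analysis sits.

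On timing, the inclusion criterion is "Male and female subjects aged 0 to 9 months (277 days) at Inclusion". Visit 3 is defined as "VISIT 3 (STUDY DAY 22-29, i.e. 21-28 DAYS AFTER TREATMENT START", whatever the child's age, and its procedures include "Perform a physical examination including body measurements and vital signs". The later in-clinic visits, 5 to 11, are fixed by age, with windows of ±14 days (Visits 5-7) or ±21 days (Visits 8-11).

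**The concern.** Growth pattern is part of the secondary objective (SAP 3.1), and protocol 9.1 names linear growth as at risk from undertreatment. Size in the first year depends strongly on age. An unadjusted comparison of raw values across a wide age range puts the age spread into the error term. With 31 children, a real difference could easily be hidden and a non-significant result misread as similar growth.

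Small numbers alone do not explain the choice. The same SAP keeps age at randomization in its mixed models for LT4 dose/kg, TSH, FT4 and the parents' questionnaire, and keeps the basal value for TSH and FT4. It also repeats the dose, TSH and FT4 comparisons separately for neonates and infants. Growth gets none of this, although SAP 3.4 itself gives fast-changing measurements related to growth as its reason for dropping LOCF.

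**Working it through.** **The plan's own figure.** There is none for growth. The only power statement (68 v 34 children, 80% power) concerns LT4 dose/kg. It reproduces: a difference of 20% × 6 = 1.2 mcg/kg/day with SD 2 gives power 0.808 at 68:34. It supplies no SD or effect size for length, weight or head circumference.

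**Inputs from the documents.** 31 randomized (SAP 3); 4 neonates, 3 v 1 (SAP 3.4), hence 27 infants; age at inclusion 0-277 days; Visit 3 at 21-28 days after treatment start.

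**Assumed inputs.** Arm totals 21:10 (2:1 ratio; actual totals not given); ages uniform within stratum; weight about 3.5 kg at birth and 9.0 kg at 300 days; within-age SD 0.9 kg; correlation with baseline weight 0.7-0.9.

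**1. Age range at Visit 3.** Youngest 0 + 21 = 21 days; oldest 277 + 28 = 305 days. These are eligibility limits, not the observed spread.

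**2. Chance age difference between arms.** The SD of age at Visit 3 is about 82 days, and √(1/21 + 1/10) = 0.384. The SE of the difference in mean age is 82 × 0.384 ≈ 31 days, or about 26 days with the neonates held at 3 v 1. Both are about as long as, or longer than, the 21-28 days of treatment being assessed.

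**3. Precision of the Visit 3 weight comparison.** Information kept = (adjusted SE / raw SE)².

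| Analysis | SE of arm difference (kg) | Information kept by the raw comparison |
|---|---|---|
| Raw | 0.51 | – |
| Age only | 0.9 × 0.384 = 0.35 | (0.346/0.51)² = 46% |
| Baseline and age | 0.15-0.25 | (0.15/0.51)² = 9% to (0.25/0.51)² = 24% |

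**4. Sensitivity to the assumptions.** With the same weights and SD but a square-root or a linear growth curve, a repeat simulation gave a raw SE of 0.47-0.60 kg and a baseline-and-age SE of 0.16-0.26 kg. The raw comparison then kept 7-27% against baseline and age, and 35-56% against age alone. A wider set (weight gain 4-6 kg over the age range, SD 0.6-1.0 kg, correlation 0.8-0.95) gave 2-22% and about 15-60%.

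**5. Type I error.** The simulated rejection rate of the Wilcoxon test under no effect was 4.1-5.5%, so it stays near 5%.

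**6. Visits 5-11.** Uniform windows give an age SD of 14/√3 = 8 days or 21/√3 = 12 days, under 4% of weight variance. What is missing is mainly baseline adjustment. In large samples it lowers the SE by 1 − √(1 − ρ²): 13% at ρ = 0.5 and 29% at ρ = 0.7. With a factor of 1 + 1/27 on the variance for estimating the slope from 31 children, the figures are 12% and 27%. A range of about 11-29% at Visit 8 is fair.

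**The case against.** The strongest defence is that this is an exploratory analysis of 31 children, and a rank test is simple and valid. That largely stands. SAP 9.4 declares all efficacy analyses explorative. Table 2 of the protocol sends only some children to Visits 5, 6, 7, 9, 10 and 11, so a model with many covariates at each visit would be fragile. SAP 9.3 compares the arms on age at randomization and on screening length, weight and head circumference, so a chance imbalance would be visible. Clinically significant growth abnormalities arising after consent are recorded as adverse events (protocol 15.2.2), so growth safety does not rest on this test.

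None of this explains why baseline and age are kept elsewhere and dropped here, or why the change is not listed.

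A reader might infer more than the documents support:

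- *The Visit 3 comparison is close to empty, or biased.* Randomization protects type I error, and against age adjustment alone the raw test keeps about 46% on the inputs above. The larger loss depends on an assumed baseline correlation.
- *Chance imbalance will decide the result, or a real effect must be missed.* For a shift of one within-age SD, simulated Visit 3 power was 15-41% raw and 66-72% age-adjusted. That is a loss of power, not a certainty either way.
- *Every visit mixes ages.* Only Visit 3 does so materially.
- *The SAP dropped sex.* Sex was not in the protocol's covariate list either.

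**Conclusion.** The point holds as a loss of precision and an undeclared departure from the protocol, not as a threat to validity. SAP 9.4.2 drops the planned basal value and age covariates for growth, and SAP 3.4 does not say so. The cost is concentrated at Visit 3, where the raw comparison keeps roughly 9-24% of the information of a baseline-and-age model and about 46% of that of an age-only model. At Visits 5-11 it is modest: about 11-29% of the SE at Visit 8 if the baseline correlation is 0.5-0.7.

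The age limits and the missing entry in SAP 3.4 come straight from the documents. The percentages do not: they rest on an assumed weight curve, within-age SD, baseline correlation, 21:10 split and uniform ages. They are for weight; length and head circumference were not calculated. Because the analysis is exploratory, this is a cheap improvement worth making before the growth tables are run, not a fault that undermines the trial's conclusions.

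**What to change.** 1. In SAP 9.4.2, analyse length, weight and head circumference by ANCOVA, or by the SAP's existing mixed model, with the baseline value and age; sex is optional. Both terms are needed on the raw scale, because baseline values are themselves taken at ages from 0 to 277 days. The alternative is age- and sex-specific z-scores adjusted for the baseline z-score.
2. Keep the raw summaries, and keep the Wilcoxon test as descriptive or supportive. Present raw Visit 3 values descriptively only.
3. Add an entry for protocol 19.3.4 to SAP 3.4, stating which planned covariates are kept, which are dropped (stratum and center), and why.

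**Cost.** SAP wording and modest programming; no new data, since age, sex and body measurements are already collected. A growth reference must be chosen if z-scores are used. Few covariates can be supported at visits attended by only a subset of the 31 children, so the list should stay at baseline and age. If the mixed model is used, a simpler covariance structure should be named in advance, because Table 2 schedules no child for both Visit 5 and Visit 10 and an unstructured matrix across all visits could not be estimated.
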